#### **12.5.7.1. Time period for detecting and recording adverse events, serious adverse events and pregnancies**

All AEs during 7 days following administration of each dose vaccination of study vaccine(s) (Day 1 to Day 7 post primary vaccination and Day 1 to Day 7 post 2nd vaccination ) must be recorded into the appropriate section of the eCRF, irrespective of intensity or whether or not they are considered vaccination-related.

All AEs/SAEs leading to withdrawal from the study will be collected and recorded from the time of the receipt of study vaccine(s)/product(s).

**CONFIDENTIAL**209141 (RSV MAT-011)  
Protocol Amendment 6 Final

SAEs that are related to the study vaccine(s) will be collected and recorded from the time of the receipt of study vaccine(s) until the subject is discharged from the study.

In addition to the above-mentioned reporting requirements and in order to fulfil international reporting obligations, SAEs that are related to study participation (i.e. protocol-mandated procedures, invasive tests, a change from existing therapy) or are related to a concurrent GSK medication/vaccine will be collected and recorded from the time the subject consents to participate in the study until she/he is discharged from the study.

The time period for collecting and recording pregnancies will begin at the receipt of study vaccine(s) and will end 181 days following administration of the dose of study vaccine(s). See section [12.5.8](#) for instructions on reporting of pregnancies.

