## CONFIDENTIAL

209141 (RSV MAT-011)  
Protocol Amendment 6 Final

Epoch	Epoch 001	Epoch 002 (Vaccination 1)			Epoch 003 (Follow-up 1)		Epoch 004 (Vaccination 2)				Epoch 005 (Follow-up 2)
Type of contact	Screening	Visit 1	Visit 2	Visit 3	Phone Contact 1		Visit 4	Visit 5	Phone Contact 2	Visit 6	Phone Contact 3
Time points	Day -7 to Day 1	Day 1	Day 8	Day 31	Day 181	Day 181 to -7 before 2 nd vaccination	Day -7 to Day of 2 nd vaccination	From 12 up to 18 months post 1 st vaccination	Day 8 post 2 nd vaccination	Day 31 post 2 nd vaccination	Day 181 post 2 nd vaccination
Sampling time points	Pre-Vacc 1	Vacc 1	Post-Vacc 1	Post-Vacc 1	Post-Vacc 1	Pre-Vacc 2	Pre-Vacc 2	Vacc 2	Post-Vacc 2	Post-Vacc 2	Post-Vacc 2
Recording of AE leading to withdrawal		●	●	●	●			●	●	●	●
Recording of serious AE 	●	●	●	●	●		●	●	●	●	●
Recording of pregnancies		●	●	●	●		●	●	●	●	●
Recording of concomitant medications/vaccinations 		●	●	●	●		●	●	●	●	●
Record any intercurrent medical conditions			●	●	●		●	●	●	●	●
Screening conclusion	●										
Investigator sign-off on eCRF before analysis	●			●	●					●	●
COVID-19 eCRFs log page							●	●	●	●	●
Study conclusion primary study					●						
Study conclusion extension											●

Vacc: vaccination

- is used to indicate a study procedure that requires documentation in the individual eCRF.
- is used to indicate a study procedure that does not require documentation in the individual eCRF

1 Date of birth (month and year or year only, as per local regulations), race, ethnicity and childbearing potential (if subject not of childbearing potential, the specific reason should be documented in the eCRF) (see Section 12.6.1.1.1 for more detail).

2 Physical examination including resting vital signs (blood pressure, heart rate and respiratory rate, temperature) measured after at least 10 minutes of rest.

Screening: Physical exam, vital signs (blood pressure, heart rate and respiratory rate, temperature), and weight, height and BMI will be recorded in the eCRF.

Visit 1: History directed physical exam will be performed and the vital signs will be recorded in the eCRF

**CONFIDENTIAL**209141 (RSV MAT-011)  
Protocol Amendment 6 Final

Visit 2 Physical examination will be performed only if deemed necessary by the investigator. If performed, only vital signs (blood pressure, heart rate and respiratory rate) will be required recorded in the eCRF

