**Table 4** **Intervals between study visits**

Interval	Optimal timing	Allowed interval
Screening Visit→ Visit 1	≤7 days	-7 - 1 days*
Visit 1 → Visit 2	8 days	7 - 10 days
Visit 1 → Visit 3	31 days	30 - 45 days
Visit 1 → Phone Contact 1	181 days	165 - 195 days
Visit 4 → Visit 5	≤7 days	-7 to 1 days*
Visit 1 → Visit 5	365 days	365 - 548 days**
Visit 5 → Phone Contact 2	8 days	7 - 10 days
Visit 5 → Visit 6	31 days	30 - 45 days
Visit 5 → Phone Contact 3	181 days	165 - 195 days

\*From 7 days prior to vaccination up to and including the day of vaccination.

\*\* For a 6-month period ≥12 to <18 months post 1st vaccination

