	
fever resulting in a medically attended visit. In addition, the prevalence of any and Grade 3 fever will be presented graphically over time after each vaccination.
 
The percentage of subjects with any unsolicited AEs during the 30-day follow-up period (the day of vaccination + 29 subsequent days) with its exact 95% CI will be tabulated by group and by Medical Dictionary for Regulatory Activities (MedDRA) system organ classes (SOC) and preferred term. Similar tabulation will be done for Grade 3 unsolicited AEs, for any causally related unsolicited AEs, for Grade 3 causally related unsolicited AEs and for unsolicited AEs resulting in a medically attended visit and leading to withdrawal from study. The verbatim term of unsolicited AEs will be reviewed by a physician and the signs and symptoms will be coded according to the MedDRA Dictionary for Adverse Reaction Terminology.
 
The percentage of subjects with at least one report of SAE classified by the MedDRA SOC and Preferred Terms and reported during the 30-day follow-up period (the day of vaccination + 29 subsequent days) will be tabulated with exact 95% CI. SAEs will also be described in detail.
 
The percentage of subjects using concomitant medication (any medication, any antipyretic and any antipyretic taken prophylactically, respectively) during the 7-day follow-up period and during the 30-day follow-up period will be summarized by each group and pooled.

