Secondary	
(US and ex-US data to be considered pooled, then separately)
 
For each group with 1st dose vaccination of RSVPreF3 (two dose level) when given alone or co-administered with dTpa; the following points will be analysed for 1st and 2nd dose vaccination.
 
The percentage of subjects with at least one local AE with at least one general AE and with any ("solicited or unsolicited") AE during the 7-day or 30 -day follow-up as well any SAE up period to 180 days post 1st and 2nd vaccination time points will be tabulated with exact 95% CI by study group. The same computations will be done for Grade 3 AEs, for any AEs considered related to vaccination, for Grade 3 AEs considered related to vaccination and for AEs resulting in medically attended visits and AEs leading to withdrawal from study.
 
The percentage of subjects with at least one report of SAE classified by the MedDRA SOC and Preferred Terms and reported during the 30-day or 180-day follow-up period will be tabulated with exact 95% CI for each formulation (US and ex-US).
 
The percentage of subjects reporting each individual solicited local AE on left or Right arms (any grade, Grade 3 and those resulting in a medically attended visit) and solicited general AE (any grade, Grade 3, any related, Grade 3 related and those resulting in a medically attended visit) during the 7-day follow-up period (i.e. on the day of vaccination and 6 subsequent days) will be tabulated based on maximum intensity for each group for each formulation (US and ex-US).
 
For fever, the number and percentage of subjects reporting fever by half degree (°C) cumulative increments during the 7-day follow-up period will be tabulated for each group for each formulation (US and ex-US). Similar tabulations will be performed for any fever with a causal relationship to vaccination, Grade 3 or above ($> 39.0^{\circ}\text{C}/102.2^{\circ}\text{F}$) causally related fever, and fever resulting in a medically attended visit. In addition, the prevalence of any and Grade 3 fever will be presented graphically over time after each vaccination.
 
For each formulation (US and ex-US), the percentage of subjects with any unsolicited AEs during the 30-day follow-up period (i.e. on the day of vaccination and 29 subsequent days) with its exact 95% CI will be tabulated by group and by Medical Dictionary for Regulatory Activities (MedDRA) SOC and preferred term. Similar tabulation will be done for Grade 3 unsolicited AEs, for any causally related unsolicited AEs, for Grade 3 causally related unsolicited AEs and for unsolicited AEs resulting in a medically attended visit. The verbatim term of unsolicited AEs will

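### AEs leading to withdrawal are collected to the Day 181 contact after each dose, but the SAP rows that report them stop at Day 30 for non-serious events

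*Protocol*

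**What the plan says.** **Collection.** Protocol 12.5.7.1 sets the start: "All AEs/SAEs leading to withdrawal from the study will be collected and recorded from the time of the receipt of study vaccine(s)/product(s". It names no end. Protocol Table 3 has a row headed "Recording of AE leading to withdrawal", marked at Visits 1, 2 and 3 and at Phone Contact 1 (Day 181), then at Visit 5, Phone Contact 2, Visit 6 and Phone Contact 3 (Day 181 after the second dose). The neighbouring row for unsolicited AEs stops at Visit 3 and Visit 6.

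**Tabulation.** The current SAP (Amendment 4), section 5.3.1, mentions these events twice.

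- In the primary safety analysis, the parent table is "The percentage of subjects with any unsolicited AEs during the 30-day follow-up period (the day of vaccination + 29 subsequent days". A similar table is then promised "for unsolicited AEs resulting in a medically attended visit and leading to withdrawal from study".
- In the secondary safety analysis, the parent row covers AEs over 7 or 30 days, "as well any SAE up period to 180 days post 1st and 2nd vaccination time points". The same calculation is then repeated "for AEs resulting in medically attended visits and AEs leading to withdrawal from study".

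The other long-window table in SAP 5.3.1, by SOC and preferred term, covers SAEs only: "reported during the 30-day or 180-day follow-up period will be tabulated with exact 95% CI for each formulation".

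**Disposition.** SAP 5.1.2 tabulates withdrawals with their reasons, by group. Protocol 9.1 lists a non-serious unsolicited AE as one of those reasons.

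**The concern.** Once the 30-day unsolicited window closes, the only non-serious AEs still being recorded are those that lead to withdrawal. The protocol keeps that collection open to Day 181, so someone evidently wants to know about them. The SAP then reports these events as sub-rows of tables that close at Day 30. What is collected and what is reported do not cover the same period.

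At stake is a descriptive tolerability row. A group could show no AEs leading to withdrawal in the AE tables while its disposition column lists a withdrawal for a non-serious AE. The reader would then have a count without the event term, grade, relatedness or dose, and no planned reconciliation between the two tables.

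**Working it through.** The plan gives no figure to reproduce. The check sets the collection period against the reporting windows.

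**1. Collection period.** Start: receipt of vaccine (Protocol 12.5.7.1). End: the Day 181 contact after each dose (Protocol Table 3). The end date rests on Table 3, because the shading of Protocol Table 14 cannot be read in the text available. Protocol Table 4 gives Phone Contact 1 and the interval "Visit 5 → Phone Contact 3" the same timing: Day 181, allowed 165 to 195.

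**2. Reporting windows.**

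| Table | Window | Would it show a non-serious AE from Day 31 on as leading to withdrawal? |
|---|---|---|
| SAP 5.3.1 primary, unsolicited AEs and its sub-tables | Days 1–30 | No |
| SAP 5.3.1 secondary, overall AE row and its repeats | 7 or 30 days; SAEs to 180 days | No |
| SAP 5.3.1 secondary, SAEs by SOC and preferred term | 30 or 180 days | No, SAEs only |
| SAP 5.3.2.3, combined solicited and unsolicited summaries | None stated | Might list the event, but not as leading to withdrawal |
| SAP 5.1.2, disposition | Whole participation | Counts the withdrawal by reason; no term, grade or relatedness |

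**3. Follow one event.** Take a non-serious AE that starts on Day 60 after the first dose and leads to withdrawal. It is recorded under the Table 3 row. It starts after Day 30, so it falls outside the primary table. It is not serious, so the 180-day extension in the secondary row does not reach it. It appears as one count in disposition. This assumes that the windows apply to the start day of the event.

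**4. Calendar share.** Days outside the 30-day window: 181 − 30 = 151 per dose, and 151/181 = 83.4%. With the contact at Day 165: 135/165 = 81.8%. At Day 195: 165/195 = 84.6%. This is a share of days, not of risk.

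**5. What one case would do.** The exact upper limit solves P(X ≤ x | n, p) = 0.025. For 0 of 100 it is 1 − 0.025^(1/100) = 3.6%, the figure in Protocol Table 18. For 1 of 100, (1 − p)^100 + 100p(1 − p)^99 = 0.025 gives 5.4%. One unreported case in a pooled group of 100 is therefore the difference between 0% (upper limit 3.6%) and 1% (upper limit 5.4%). This is an illustration, not a forecast.

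**The case against.** The case on the other side is substantial, and most of it stands.

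- **The withdrawal is not lost.** Disposition counts it by reason, and Protocol 9.1 requires withdrawals for AEs to be kept distinct from the rest. A reader might infer that such an event appears nowhere. The documents do not support that: the combined summaries in SAP 5.3.2.3 state no window, and the list of tables and listings is a separate document (SAP 10.2) that was not available.
- **There is little left to withdraw from.** After Visit 3, and again after Visit 6, one phone call remains, with no dose and no blood sample. Protocol 9.1 defines withdrawal by absence from the concluding contact, so a woman who takes the call has not withdrawn. Both visits may fall as late as Day 45, or later under the special-circumstances intervals, so a visit can still be outstanding shortly after Day 30. That does not change the expectation of very few cases.
- **It is not a declared endpoint.** AE endpoints run to Day 31 and only SAEs to Day 181. Protocol 10.3.4 plans no table of AEs leading to withdrawal; the SAP added these rows. That makes this an improvement to a descriptive table, not a failed planned analysis.
- **The wording of the primary text.** One could read it as counting only AEs that were both medically attended and led to withdrawal. That is strained, since the secondary text lists the two as separate items.

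What does not fall is the mismatch itself. The 180-day extension in the secondary row is attached to SAEs, so a programmer following SAP 5.3.1 as written would close the withdrawal row at Day 30 for non-serious events.

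**Conclusion.** The concern holds in a limited form and is minor. Non-serious AEs that start after Day 30 and lead to withdrawal are collected to Day 181 after each dose. No AE table with a stated window would show them as leading to withdrawal, with term, grade and relatedness; disposition would still count them by reason.

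The number affected is likely very small and possibly zero. The documents give no rate for it. The planned 5% drop-out (Protocol 5.3; 25 of 500) covers every reason, so it cannot be turned into a count of late AE withdrawals without an unsupported assumption. Nor does the 83% calendar share measure how many such events are missed.

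The conclusion rests on two readings: that Table 3 sets the end of collection, and that the rows in SAP 5.3.1 take the windows of the tables they repeat. No objective, primary endpoint or decision rule is affected.

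**What to change.** In SAP 5.3.1, give AEs leading to withdrawal, serious and non-serious, a row of their own:

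- by group, from each dose through the Day 181 contact after that dose (Phone Contact 1 and Phone Contact 3);
- separate from medically attended AEs, which also removes the ambiguous wording in the primary text;
- with SOC and preferred term, grade and relatedness;
- reconciled with the AE reasons in the disposition table of SAP 5.1.2.

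The cost is one SAP sentence and one extra descriptive row or table. No new data are needed, and the second and final analyses in SAP 7.1.1 are already timed to the two Day 181 contacts.

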#### **12.5.7.2. Evaluation of adverse events and serious adverse events**

##### **12.5.7.2.1. Active questioning to detect adverse events and serious adverse events**

As a consistent method of collecting AEs, the subject should be asked a non-leading question such as:

*'Have you felt different in any way since receiving the vaccine(s) or since the previous visit?'*

When an AE/SAE occurs, it is the responsibility of the investigator to review all documentation (e.g. hospital progress notes, laboratory and diagnostics reports) relative to the event. The investigator will then record all relevant information regarding an AE/SAE in the eCRF. The investigator is not allowed to send photocopies of the subject's medical records to GSK instead of appropriately completing the eCRF. However, there may be instances when copies of medical records for certain cases are requested by GSK. In this instance, all subject identifiers will be blinded on the copies of the medical records prior to submission to GSK.

The investigator will attempt to establish a diagnosis pertaining to the event based on signs, symptoms, and/or other clinical information. In such cases, the diagnosis should be documented as the AE/SAE and not the individual signs/symptoms.

CONFIDENTIAL

209141 (RSV MAT-011)  
Protocol Amendment 6 Final**12.5.7.2.2. Assessment of adverse events***Assessment of intensity*

The intensity of the following solicited AEs will be assessed as described:

**Table 25      Intensity scales for solicited symptoms in adults and children of 6 years of age or more**

Adults/Child ( $\geq 6$ years)		
Adverse Event	Intensity grade	Parameter
Pain at injection site	CCI - This section contained Clinical Outcome Assessment data collection questionnaires or indices, which are protected by third party copyright laws and therefore have been excluded.	
Redness at injection site		
Swelling at injection site		
Temperature*		
Headache		
Fatigue		
Gastrointestinal symptoms (nausea, vomiting, diarrhoea and/or abdominal pain)		
CCI - This section contained Clinical Outcome Assessment data collection questionnaires or indices, which are protected by third party copyright laws and therefore have been excluded.		

The maximum intensity of local injection site redness/swelling will be scored at GSK Biologicals according to the standard GSK Biologicals' scoring system for adults:

CCI - This section contained Clinical Outcome Assessment data collection questionnaires or indices, which are protected by third party copyright laws and therefore have been excluded.

The investigator will assess the maximum intensity that occurred over the duration of the event for all unsolicited AEs (including SAEs) recorded during the study. The assessment will be based on the investigator's clinical judgement.

**CONFIDENTIAL**209141 (RSV MAT-011)  
Protocol Amendment 6 Final

The intensity should be assigned to 1 of the following categories:

CCI - This section contained Clinical Outcome Assessment data collection questionnaires or indices, which are protected by third party copyright laws and therefore have been excluded.

An AE that is assessed as Grade 3 CCI should not be confused with a SAE. Grade 3 is a category used for rating the intensity of an event; and both AEs and SAEs can be assessed as Grade 3. An event is defined as 'serious' when it meets 1 of the pre-defined outcomes as described in Section 12.5.2.

#### *Assessment of causality*

The investigator is obligated to assess the relationship between study vaccine(s) and the occurrence of each AE/SAE using clinical judgement. In case of concomitant administration of multiple vaccines/products, if possible, the investigator should specify if the AE could be causally related to a specific vaccine/product administered (i.e. investigational, control/placebo or co-administered vaccine). When causal relationship to a specific vaccine(s) cannot be determined, the investigator should indicate the AE to be related to all products.

Alternative plausible causes, such as natural history of the underlying diseases, concomitant therapy, other risk factors, and the temporal relationship of the event to the study vaccine(s) will be considered and investigated. The investigator will also consult; for the RSV maternal vaccine the IB; and for the *Boostrix* Vaccine, the SmPC and/or Prescribing Information to determine his/her assessment.

There may be situations when a SAE has occurred and the investigator has minimal information to include in the initial report to GSK. However, it is very important that the investigator always makes an assessment of causality for every event prior to submission of the Expedited Adverse Events Report to GSK. The investigator may change his/her opinion of causality in light of follow-up information and update the SAE information accordingly. The causality assessment is one of the criteria used when determining regulatory reporting requirements.

All solicited local (injection site) reactions will be considered causally related to vaccination. Causality of all other AEs should be assessed by the investigator using the following question:

**CONFIDENTIAL**

209141 (RSV MAT-011)  
 Protocol Amendment 6 Final

*Is there a reasonable possibility that the AE may have been caused by the study vaccine?*

YES : There is a reasonable possibility that the study vaccine(s) contributed to the AE.

NO : There is no reasonable possibility that the AE is causally related to the administration of the study vaccine(s). There are other, more likely causes and administration of the study vaccine(s) is not suspected to have contributed to the AE.

If an event meets the criteria to be determined as 'serious' (see Section 12.5.2), additional examinations/tests will be performed by the investigator in order to determine ALL possible contributing factors for each SAE.

Possible contributing factors include:

- Medical history.
- Other medication.
- Protocol required procedure.
- Other procedure not required by the protocol.
- Lack of efficacy of the vaccine(s)/product(s) (delete as applicable), if applicable.
- Erroneous administration.
- Other cause (specify).

*Assessment of outcomes*

The investigator will assess the outcome of all unsolicited AEs (including SAEs) recorded during the study as:

- Recovered/resolved.
- Recovering/resolving.
- Not recovered/not resolved.
- Recovered with sequelae/resolved with sequelae.
- Fatal (SAEs only).

**12.5.7.2.3. Medically attended visits**

For each solicited and unsolicited symptom the subject experiences, the subject will be asked if she received medical attention defined as hospitalisation, or an otherwise unscheduled visit to or from medical personnel for any reason, including emergency room visits. This information will be recorded in the eCRF.

**CONFIDENTIAL**209141 (RSV MAT-011)  
Protocol Amendment 6 Final**12.5.8. Reporting of serious adverse events, pregnancies, and other events****12.5.8.1. Prompt reporting of serious adverse events, pregnancies, and other events to GSK**

SAEs that occur in the time period defined in Section 12.5.7 will be reported promptly to GSK within the timeframes described in [Table 15](#), once the investigator determines that the event meets the protocol definition of a SAE.

Pregnancies that occur in the time period defined in Section 12.5.7 will be reported promptly to GSK within the timeframes described in [Table 15](#), once the investigator becomes aware of the pregnancy.

